8.2.1 Dispensing of Vadadustat

Subjects will be provided with a supply of vadadustat at the Baseline visit according to the IWR system assignment. Resupply of additional vadadustat at subsequent visits will be managed via

the IWR system and will be dependent on the current dose level of vadadustat and the number of tablets remaining in the subject's current vadadustat supply at a given study visit ([Section 8.4.4.1, Vadadustat Dosing and Dose Adjustment Algorithms](#)). Subjects will be instructed to finish 1 bottle before opening a new bottle.

At the Baseline visit, study subjects will be provided with 1 bottle of vadadustat. Each bottle of vadadustat will contain 100 tablets of vadadustat (150 mg/tablet).

Subjects should be instructed to bring unused vadadustat and empty bottles to each study visit for product accountability. Empty bottles will be collected at these study visits. Previously dispensed bottles (whether opened or unopened) with remaining tablets may be redispensed to the subject during the dosing phase of the study.

A Vadadustat Dosing Information Sheet will be provided to the subject at dispensing of study medication.

8.2.2 Dispensing of Darbepoetin Alfa

Darbepoetin alfa will be dispensed according to the IWR system assignment.

- For subjects already on darbepoetin alfa, the initial dosing regimen in the study should be based on the prior dosing regimen.

Dispensing of additional darbepoetin alfa at subsequent dosing visits will be managed by the IWR system ([Section 8.4.4.2, Darbepoetin Alfa Dosing and Dose Adjustment Algorithms](#)).

Darbepoetin alfa doses may be self-administered or staff administered at the site facility or by the subject at home according to the Investigator's determination and local practice.

Subjects should be instructed to bring the darbepoetin alfa boxes to each study visit for drug accountability. There will be no physical accountability performed with used syringes. The investigative site will maintain site drug accountability records of the actual syringes dispensed and used by a subject.

A Darbepoetin Alfa Dosing Information Sheet will be provided to the subject at dispensing of study medication.

8.3 Product Accountability and Destruction

Product accountability should be an ongoing process throughout the study. All study medication (vadadustat and darbepoetin alfa) must be accounted for and any discrepancies explained. The Investigator or designated study personnel are responsible for keeping accurate records of the clinical supplies received from the Sponsor, all supplies retained in inventory at the investigative site, and study medication dispensed to or returned from each subject. Records will be maintained that accurately reflect the drug accountability of vadadustat and darbepoetin alfa at all times.

Proper drug accountability includes, but is not limited to:

- Continuously monitoring expiration dates if expiry date or retest date is provided to the Investigator.
- Frequently verifying that actual inventory matches documented inventory.

- Verifying that the log is completed for all drug received and that all required fields are complete, accurate, and legible.

If any dispensing errors or discrepancies are discovered, the Sponsor must be notified immediately.

During the study, the Investigator will be notified of any expiry dates or retest date extensions of clinical study material. If an expiry date notification is received during the study, the investigative site must complete all instructions outlined in the notification, including segregation of expired clinical study material for return to the Sponsor or its designee for destruction.

Prior to investigative site closure and at appropriate intervals during the study, a representative from the Sponsor will perform clinical study material accountability and reconciliation.

At the end of the study, the Investigator will retain all original documentation regarding clinical study material accountability, return, and/or destruction, and copies will be sent to the Sponsor.

All unused and/or partially used vadadustat or darbepoetin alfa should be returned to the Sponsor or destroyed at the investigational site, as specified by the Sponsor. Appropriate records of the disposal will be documented and maintained. No unused vadadustat or darbepoetin alfa may be disposed of until fully accounted for by the Sponsor's monitor (or designee). Empty containers may be disposed of according to local procedures.

8.4 Treatment of Subjects

8.4.1 Treatment Group Assignments

Subjects will be randomized in a 1:1 ratio via the IWR system to either:

- Vadadustat (starting dose of 2 tablets once daily [300 mg/day]).
- Darbepoetin alfa IV/SC (starting dose based on the current PI for investigational sites in the US and the SmPC for all other investigational sites [non-US] for adult patients with CKD on dialysis).
 - For subjects already on darbepoetin alfa, the initial dosing regimen in the study should be based on the prior dosing regimen.

Target enrollment for each treatment group is approximately 150 subjects.

8.4.2 Randomization

This study will be open to approximately 300 subjects with incident DD-CKD with Hb between 8.0 and 11.0 g/dL (inclusive).

Using an IWR system, eligible subjects will be assigned using permuted block randomization and a 1:1 ratio to either vadadustat or darbepoetin alfa during their Baseline visit.

To maintain balance between vadadustat-treated and darbepoetin alfa-treated subjects, randomization will be stratified with respect to: 1) geographic region (US versus EU versus ROW); 2) New York Heart Association CHF Class (0 [no CHF] or I versus II or III); and 3) study entry Hb level (<9.5 or \geq 9.5 g/dL).

8.4.3 Blinding

This will be an open-label study. Treatment assignment will be done through the IWR system and the Investigator, Sponsor, and CRO study teams will not be aware of which treatment will be assigned next. Treatments will be administered in an open-label fashion.; The Sponsor and CRO study teams will be blinded to ‘by treatment’ aggregated analyses except for the unblinded statistician. Because Hb values are objective and will be measured via a central laboratory for all efficacy endpoints, efficacy assessments are not considered to be subject to bias with an open-label design. In addition, the study will involve blinded adjudication of MACE, the use of an IDMC, and an identical schedule of visits, procedures, and assessments for both treatment groups in order to reduce the potential for bias. However, certain personnel directly involved in medical oversight of the study, regulatory reporting of safety information, and on-site monitoring activities may become unblinded to the treatment assignments of individual subjects during the course of the study. In addition, in order to reduce subjectivity of dose adjustment, adjustments to doses for vadadustat and darbepoetin alfa will be based on Hb concentration and Dose Adjustment Algorithms.

The EAC will remain blinded throughout the full course of the study.

8.4.4 Dosing and Dose Adjustment Guidelines

Dosing will be initiated at the Baseline visit, and the first dose of study medication (vadadustat or darbepoetin alfa) will be administered at the investigative site after other Baseline visit procedures have been completed. The Investigator may elect to postpone the initial dose of study medication until a subsequent visit based on the subject’s Hb level or Hb trajectory assessed at the Baseline visit, or based on timing of the last ESA dose given during screening.

Year 1-4 Treatment Period Visits

Hemoglobin will be monitored via HemoCue throughout the study to determine if the dose of study medication (vadadustat or darbepoetin alfa) will be adjusted, interrupted, or maintained. From Weeks 0 to 12, Hb will be obtained via HemoCue every 2 weeks for monitoring for dose adjustment. From Week 12 to Week 52, Hb will be monitored every 4 weeks via HemoCue.

From Week 53 through the study end, Hb will continue to be monitored via HemoCue to determine if the dose of study medication will be adjusted, interrupted, or maintained. Any unscheduled measurement between study visits will be recorded in the appropriate CRF and the subject’s source when a HemoCue value is taken. Hemoglobin will also be assessed with a CBC through the central laboratory for efficacy and safety evaluations; however, dose adjustments should be based on the HemoCue Hb value. If the Investigator has an immediate clinical concern about a subject’s HemoCue value, the Investigator may use clinical judgement and repeat the HemoCue Hb, use local lab values or wait for central lab results. The test method utilized to inform the treatment decision must be recorded in the appropriate CRF and the subject’s source.

Year 2-4 Monthly Hb Monitoring

Additionally, after Week 52 through study end, the Hb drawn as part of the local standard of care labs must be monitored monthly for dosing oversight. Per the dosing algorithms, if the Hb value suggests a dose adjustment is needed, an unscheduled visit must be performed.

If monthly standard of care labs are not available, a study unscheduled visit must be performed. This visit will include, at minimum, the Hb measurement via HemoCue, dose adjustment assessment, and adverse events assessment.

The monthly Hb monitoring method is flexible between study visits after Week 52 to minimize unnecessary travel or redundant blood sampling for the subject.

The aim is to increase to or maintain a Hb level of 10.0 g/dL to 11.0 g/dL in the US and 10.0 g/dL to 12.0 g/dL outside of the US throughout the study.

Dose adjustments for vadadustat and darbepoetin alfa will be guided by Hb concentration and Dose Adjustment Algorithms. The Dose Adjustment Algorithm for darbepoetin alfa will follow the PI for investigational sites in the US and the SmPC for all other sites (non-US) for adult patients with CKD on dialysis.

This protocol provides guidance for the treatment of subjects with anemia associated with CKD in order to achieve and maintain Hb levels within the target Hb range. Dose adjustment should be based on the Investigator's clinical discretion, incorporating the protocol guidance and considering the subject's clinical condition, Hb rate of rise, Hb rate of decline, Hb variability and ESA responsiveness. In cases where the Investigator does not follow the dosing algorithm, the clinical circumstances must be documented in the subject's source.

8.4.4.1 Vadadustat Dosing and Dose Adjustment Algorithms

Subjects assigned to vadadustat will initiate dosing at 2 tablets taken orally once daily (300 mg/day). Dose levels of vadadustat utilized in this study include 150, 300, 450, and 600 mg (available tablet strength is 150 mg).

Dosing will be initiated at the Baseline visit and the first dose of vadadustat will be administered at the investigative site after other Baseline visit procedures have been completed. The Investigator may elect to postpone the initial dose of study medication until a subsequent visit based on the subject's Hb level or Hb trajectory assessed at Baseline, or based on timing of the last ESA dose given during screening. Thereafter, vadadustat will be taken once daily on an outpatient basis. Subjects may take vadadustat with or without food and should be instructed to swallow the tablet(s) whole, without chewing. Subjects should be instructed to take vadadustat at roughly the same time each day.

During the study, vadadustat should be dosed according to the Dose Adjustment Algorithms ([Appendix B: Vadadustat Dosing and Dose Adjustment Algorithms](#)).

8.4.4.2 Darbepoetin Alfa Dosing and Dose Adjustment Algorithms

Subjects who are randomized to receive darbepoetin alfa will be dosed with starting doses based on the current PI for investigational sites in the US and the SmPC for all other investigational sites (non-US) for adult patients with CKD on dialysis. For subjects already on darbepoetin alfa, the initial dosing regimen in the study should be based on the prior dosing regimen. Dose adjustments will be based on the Dose Adjustment Algorithms ([Appendix C: Darbepoetin Alfa Dosing and Dose Adjustment Algorithms](#)).

In general, darbepoetin alfa will be dosed intravenously for subjects on chronic hemodialysis and subcutaneously for subjects receiving peritoneal dialysis and in accordance with the approved product label. Each subject will receive their first dose of darbepoetin alfa at the Baseline visit.

The Investigator may elect to postpone the initial dose of study medication until a subsequent visit based on the subject's Hb level or Hb trajectory assessed at Baseline, or based on timing of the last ESA dose given during screening.

Following dose conversion, darbepoetin alfa will be dosed IV or SC, with dose adjustments guided by the Dose Adjustment Algorithm ([Appendix C: Darbepoetin Alfa Dosing and Dose Adjustment Algorithms](#)). Subsequent administration of darbepoetin alfa may occur at the clinic/investigative site or may be self-administered at home per regional standard-of-care and/or based on dialysis modality (hemodialysis or peritoneal dialysis). Darbepoetin alfa dosing is independent of the visit schedule, and the dosing schedule may shift per local standard-of-care, the patient's dialysis schedule and per Investigator's discretion.

8.4.5 Late or Missed Doses

Subjects on vadadustat should be instructed to take the study medication at roughly the same time each day. If a dose is forgotten, subjects should be instructed to take the dose as soon as they remember during the same day. If a forgotten dose is not remembered on the same day, the subject should skip the dose and resume the normal dosing schedule the following day. Subjects should not double-up on missed doses.

Subjects on darbepoetin alfa should be instructed to take the study medication, including handling of late or missed doses, as described in the PI or SmPC.

Subjects should be questioned regarding dosing compliance and whether they have questions or have experienced any problems related to the dosing of study medication (vadadustat or darbepoetin alfa).

8.4.6 Iron Supplementation

Investigators will prescribe iron supplementation (IV, oral, or intradialytic) during the study to maintain ferritin ≥ 100 ng/mL or TSAT $\geq 20\%$.

Important: Because of the potential for iron to reduce the bioavailability of vadadustat, the study medication is not to be administered concurrently with an oral iron supplement (including multivitamins containing iron), iron containing phosphate binders, or any other medications containing iron. The subject should be instructed to take these medications at least 2 hours before or 2 hours after the dose of vadadustat.

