5.3 Secondary Efficacy Endpoints

The key secondary efficacy endpoints include the following:

- Mean change in Hb value between Baseline (mean pretreatment Hb) and the secondary evaluation period (Weeks 40 to 52).
- Proportion of subjects with Hb values within the target range during the primary evaluation period (Weeks 24 to 36).
- Proportion of subjects with Hb values within the target range during the secondary evaluation period (Weeks 40-52).

Other secondary efficacy endpoints include:

- Proportion of time with Hb values within the target range during the primary evaluation period (Weeks 24-36).
- Proportion of time with Hb values within the target range during the secondary evaluation period (Weeks 40-52).
- Proportion of subjects with Hb increase of >1.0 g/dL from Baseline.
- Time to achieve Hb increase of >1.0 g/dL from Baseline.

- Mean change in Hb between Baseline (mean pretreatment Hb) and the primary evaluation period (mean Hb from Weeks 24-36) stratified by pre-Baseline ESA exposure.
- Proportion of subjects receiving RBC transfusion(s) from Baseline to Week 52.
- Proportion of subjects receiving IV iron therapy from Baseline to Week 52.
- Mean monthly dose of IV elemental iron administered from Baseline to Week 52 in subjects who have received IV iron.
- ESA rescue.
- Dose adjustments from Baseline to Week 52.

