7.2 Inclusion Criteria

Subjects must meet all of the following inclusion criteria to be eligible:

1. ≥ 18 years of age.
2. Initiated chronic maintenance dialysis (either peritoneal or hemodialysis) for end-stage kidney disease within 16 weeks prior to Screening.
3. Mean screening Hb between 8.0 and 11.0 g/dL (inclusive), as determined by the average of 2 Hb values measured by the central laboratory during Screening.
4. Serum ferritin ≥ 100 ng/mL and transferrin saturation (TSAT) $\geq 20\%$ at Screening.
5. Folate and vitamin B₁₂ measurements \geq lower limit of normal (LLN) at Screening.
6. Understands the procedures and requirements of the study and provides written informed consent and authorization for protected health information disclosure.

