9.3.5 Year 1 Treatment Period Visits (Day 2 through Week 52)

During the Year 1 Treatment Period visits at Weeks 2, 4, 6, 8, 10, 12, 16, 20, 24, 28, 32, 36, 40, 44, 48, and 52, the following activities/procedures will be performed:

- Vital signs including heart rate and blood pressure (assessed in seated position after 5 minutes of rest and prior to blood draws).
- Dry weight (Weeks 12, 24, 36, and 52).
- Laboratory procedures:
 - CBC (Weeks 2, 4, 6, 8, 10, 12, 16, 20, 24, 28, 32, 36, 40, 44, 48, and 52; differential at Weeks 28 and 52).
 - Reticulocyte count (Weeks 4, 12, 28, and 52).
 - Serum chemistry (Weeks 28 and 52).
 - Liver function tests (Weeks 4, 8, 12, 16, 20, 24, 28, 36, 44, and 52).
 - Iron indices (Weeks 4, 8, 12, 20, 28, 36, 44, and 52).
 - Lipid profile (Weeks 28 and 52).
 - EPO (Weeks 4, 12, 28, and 52).
 - CRP (Weeks 28 and 52).
 - Biomarkers (Weeks 12, 28, and 52).
 - PK (Weeks 4, 12, 28, and 52; see [Section 9.2.2, Laboratory Evaluations](#); samples to be drawn only for subjects randomized to vadadustat).
 - Exploratory samples (Weeks 28 and 52).
- Record date and time of subject's last dose of vadadustat prior to the PK sample (Weeks 4, 12, 28, and 52).
- Safety assessments:
 - AE assessment.
 - RBC transfusions and ESA rescue
 - Therapeutic phlebotomy
 - MACE endpoint questionnaire.
- Medication assessments and procedures:
 - Review of concomitant medications.
 - Hb by HemoCue for dose adjustment.
 - Assess:
 - Hemodialysis vascular access type use changes.
 - Renal replacement therapy changes.
 - Dialysis adequacy, as available from local collection.
 - Drug reconciliation: Study medication (vadadustat or darbepoetin alfa) reconciliation will be conducted per the pharmacy manual instructions.
 - Visit registration in IWR.
 - Vadadustat dispensing as needed per [Section 8.2.1, Dispensing of Vadadustat](#).
 - Darbepoetin alfa dispensing.
 - Iron supplementation as needed to maintain ferritin \geq 100 ng/mL or TSAT \geq 20% (per local product label; see [Section 8.4.6, Iron Supplementation](#)).

- Question subject regarding dosing compliance and whether they have questions or have experienced any problems related to the dosing of study medication (vadadustat or darbepoetin alfa).

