- [bb] The dose will be adjusted in accordance with the Dose Adjustment Algorithms. Changes to dose will be accomplished by changing the number of tablets to be taken per day.
- [cc] Iron supplementation (IV, oral, or intradialytic) will be prescribed during the study to maintain ferritin ≥ 100 ng/mL or TSAT $\geq 20\%$. Subjects who fail to qualify for the study based on low TSAT, ferritin, folate, or B₁₂ values may receive replacement therapy based on the investigative sites' standard of care during the screening period and retest the laboratory parameter(s). Subjects who receive iron replacement therapy may retest screening Hb a minimum of 3 weeks after completion of iron replacement therapy. Vadamustat is not to be administered concurrently with oral iron supplement (including multivitamins containing iron), iron containing phosphate binders, or any iron containing medications. Oral iron supplement should be taken at least 2 hours before or 2 hours after the dose of study medication.
- [dd] End of Study (EOS) status will be done to capture subject status at the global completion of the study or at the time of withdrawal of consent or when subject deemed LTFU or death. Subjects active on the study (including those permanently discontinued from study medication and are being followed) will complete the Follow-up visit. For subjects active on the study medication at global study completion, the EOS status will be collected at the Follow-up visit. For subjects that have permanently discontinued study medication and are being followed until global study completion, the

Study Period	Optional Pre-screen	Screening	BL/ rand. [a]	Treatment Period																				Post Treatment						
				Year 1												Year 2				Year 3/Year 4										
Visit	PS	SV1	SV2	1	2	3	4	5	6	7	8	9	10	11	12	13	14	15	16	17	18	19	20	21	22/ 26	23/ 27	24/ 28	25/ 29	End of Trtmt	Follow-up [b]
Week		-8 to 0		0	2	4	6	8	10	12	16	20	24	28	32	36	40	44	48	52	64	76	88	104	116/ 168	128/ 180	140/ 192	156/ 208	EOT [c]	EOT +4 wks [dd]

EOS status will be as collected, which includes activities outlined at the Follow-up visit.

[figure not shown]

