- Section 8.4.4 Dosing and Dose Adjustment Guidelines was revised to guide Investigators to follow printed dose adjustment algorithms in lieu of IWR-programmed dosing recommendations due to some aspects of IWR-programmed dosing instructions not operating as planned. Also, updated guidance to Investigators to use clinical judgement and other Hb data to appropriately dose subjects in cases of clinical concern regarding HemoCue value. Clarification was added that after a subject completes ESA rescue, the investigator has the option to resume study medication at the same dose as previously used or with one dose higher. Monthly Hb monitoring for dosing oversight in Year 2-4 was also added to this section.

- Section 8.4.6 Iron Supplementation was updated to align with published guidelines to prescribe iron supplementation during the study when serum ferritin is less than 100 mcg/L or when serum transferrin saturation is less than 20%.
- Section 8.4.7.1 ESA Rescue (Optional) was updated to align with published guidelines raising the threshold of Hb to 9.5 for initiation of ESA rescue and permitting Investigator to initiate rescue when medically necessary even if protocol defined criteria is not met.
- Section 8.4.9 Dosing Compliance was updated to specify a range of 80-120% which is commonly used in clinical trials with oral products.
- Section 8.5 Prior and Concomitant Therapy was updated to clarify if the duration of the screening period is less than 30 days, all medications taken within 30 days prior to first dose of study medication will be recorded and that ESA dosing history for a minimum of 8 weeks prior to Baseline will be recorded.
- Section 9.3.6 Year 2-4 Monthly Hb monitoring was updated to require monthly monitoring of Hb drawn as part of local standard of care labs or via an unscheduled visit.
- Section 10.1.2 Serious Adverse Events was updated to require all new and recurrent malignancies (with a few exceptions) to be reported as a Serious Adverse Events (SAEs) to standardize reporting. If a subject develops basal cell carcinoma of skin, squamous cell carcinoma, or cervical carcinoma in situ during the study, or has worsening of these events from Baseline, the Investigator will determine if the event is reported as an AE or SAE.
- Section 10.5 was added to define overdose of study drugs.
- Section 11.1.1 Sample Size for Primary Efficacy Endpoint was updated to reflect a change in the non-inferiority margin from -0.5 g/dL to -1.0 g/dL

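### The on-study iron goal joins ferritin and TSAT with 'or', so taken literally it calls for iron only when both are low and gives no trigger when one is low

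*Protocol*

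**What the plan says.** Section 8.4.6 (Iron Supplementation) of the current protocol instructs investigators to prescribe iron during the study to maintain ferritin at or above "100 ng/mL or TSAT" at or above 20%. The same 'or' appears in the synopsis, Section 6.1, Sections 9.3.4, 9.3.5, 9.3.7 and 9.3.8, the Appendix A table row and Appendix A footnote [cc]: nine places in all.

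Some repeats are softer. Section 9.3.5, for example, reads "Iron supplementation as needed to maintain ferritin" and adds a reference to the local product label. Section 8.4.6 itself carries neither qualifier.

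Inclusion criterion 4 (Section 7.2) uses 'and': it requires serum ferritin of at least "100 ng/mL and transferrin saturation (TSAT") of at least 20% at Screening.

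The Amendment 3 entry in Appendix E records the purpose of the change to Section 8.4.6 as giving iron "when serum ferritin is less than 100 mcg/L or when serum transferrin saturation is less than 20"%. The entries for Amendments 4 to 6 do not list Section 8.4.6.

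Two of the other secondary efficacy endpoints in Section 5.3 measure iron use: "Proportion of subjects receiving IV iron therapy from Baseline to Week 52" and "Mean monthly dose of IV elemental iron administered from Baseline to Week 52 in subjects who have received IV iron".

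**The concern.** A trigger and a maintenance goal are logical opposites. If iron is to be given when either index is low, the goal is that both are adequate. A goal that either is adequate corresponds to a much narrower trigger, namely that both are low. The protocol states the second form in the section that governs iron treatment.

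Iron deficiency is named in the background section as one cause of anemia in chronic kidney disease, so repletion is part of how these subjects are treated. The indices are measured at eight post-Baseline visits in Year 1 (Weeks 4, 8, 12, 20, 28, 36, 44 and 52), and the rule comes into play each time. A site that follows the text exactly would see no prompt to treat a subject with one low index; a site that follows habit or the local label would treat. At stake are adequate iron treatment of individual subjects, consistency between sites, and the clarity of the two IV-iron endpoints.

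**Working it through.** No sample-size, power or event figure bears on this point, so there is none to reproduce. The check is one of logic.

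**Inputs.**
- On-study goal (Section 8.4.6): ferritin ≥100 ng/mL OR TSAT ≥20%.
- Entry rule (Section 7.2, criterion 4): ferritin ≥100 ng/mL AND TSAT ≥20%.
- Direct trigger (the purpose recorded in Appendix E, Amendment 3): ferritin <100 OR TSAT <20%. The log's mcg/L and the protocol's ng/mL are the same unit.

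**Step 1: turn the goal into a trigger.** Iron is called for when the goal is not met:

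NOT (ferritin ≥100 OR TSAT ≥20) = ferritin <100 AND TSAT <20.

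**Step 2: do the same for the entry rule.** Criterion 4 is failed when:

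NOT (ferritin ≥100 AND TSAT ≥20) = ferritin <100 OR TSAT <20.

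This is the same as the direct trigger.

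**Step 3: compare across the four states.**

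| Ferritin | TSAT | Meets criterion 4 | Iron called for by the 'or' goal | Iron called for by the direct trigger |
|---|---|---|---|---|
| adequate | adequate | yes | no | no |
| adequate | low | no | no | yes |
| low | adequate | no | no | yes |
| low | low | no | yes | yes |

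The 'or' goal calls for iron in 1 of 4 states and the direct trigger in 3 of 4. They differ only in the two rows where exactly one index is low. These are counts of logical states, not of subjects.

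**Step 4: an example.** Ferritin 500 ng/mL with TSAT 12% is the second row. The subject fails criterion 4 at Screening. On study, ferritin alone satisfies the goal, so Section 8.4.6 prompts nothing.

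**Step 5: how firmly the nine places bind.**
- Qualified by need: Sections 9.3.4 and 9.3.5 and the Appendix A row (3).
- Qualified by the local product label: Sections 9.3.4, 9.3.5, 9.3.7 and 9.3.8 (4).
- At least one of these qualifiers: 5.
- Neither: the synopsis, Section 6.1, Section 8.4.6 and footnote [cc], so 9 − 5 = 4.

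The synopsis and Section 6.1 also let subjects continue existing oral iron and allow oral iron under local practice in peritoneal dialysis. Footnote [cc] hangs on a table row that does carry the need qualifier. Section 8.4.6, the section the visit schedules refer back to, is the barest statement.

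**The case against.** The strongest reply is that nothing in the current text contradicts itself. The goal says 'or' in all nine places, while criterion 4 governs entry. An entry rule may properly be stricter than a maintenance rule, and the superseded protocol in the same file used 'and' on study, so the move to 'or' could have been deliberate. This stands in part: the contrast with criterion 4 does not by itself prove an error.

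A second reply concerns the amendment log, since a difference between a log and the current text is not an error. That is right, and the log is not used as proof. It describes the wording still in force, no later entry lists the section, and the purpose it gives is the either-low trigger. It therefore makes a slip in converting a trigger to a goal more likely than a deliberate loosening. The literal consequence of Section 8.4.6 follows without it.

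A reader might also infer that footnote [cc] contradicts itself, because the 'or' goal is followed by a sentence opening "Subjects who fail to qualify for the study based on low TSAT, ferritin, folate, or B". It does not. That sentence permits correction of an eligibility failure during screening; the one before it concerns treatment during the study.

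Last, the replacement rule has its own risk. Section 4.3 reports that vadadustat raises total iron-binding capacity (TIBC) and lowers ferritin, so a trigger on either index could prompt more iron in one arm. This stands, and it belongs with the cost of the fix.

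**Conclusion.** The point holds as a minor correction to a stated rule. Section 8.4.6 and its repeats, read as written, give no trigger for iron when exactly one index is low, although a subject in that state would not have qualified for the study. The plausible consequences are under-treatment of some subjects and uneven iron use between sites, with some noise in two of the ten other secondary efficacy endpoints, neither of them key secondary.

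The size cannot be given. The protocol does not report how often exactly one index is low, or how many sites would apply the text literally, and any count of subjects would rest on invented inputs.

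Three stronger readings are tempting and are not supported:
- **That the protocol bars iron when one index is low.** It does not; need, local labels, local practice and continued oral iron all remain open.
- **That the wording biases the comparison between arms.** Treatment is open-label and the drug moves the iron indices, but the same rule applies to both arms and nothing shows a direction.
- **That the primary hemoglobin endpoint, MACE or power is affected.** No such effect is shown, and no sample-size assumption depends on the iron rule.

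The conclusion assumes only that some sites will take the sentence at its word.

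**What to change.** In Section 8.4.6 and the eight repeats, replace the goal with a direct trigger: prescribe iron when ferritin is <100 ng/mL or TSAT is <20%, subject to the local label and the investigator's judgment on iron overload. Restoring 'and' in the goal is logically equivalent, but a trigger is harder to misread. Send sites a short notice of the change.

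The cost is a text edit in nine places and the notice, with no new data, visits or analyses. The downside is somewhat more iron prescribing, possibly unequal by arm because of the drug's effect on TIBC and ferritin. The size of any imbalance is unknown. It should be kept in mind when interpreting the two IV-iron endpoints, and also the exploratory endpoint in Section 5.5 on target hemoglobin without iron overload.
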